### *Subgroup Analyses*

The primary outcome analysis will be additionally performed in each of the below subgroups.

- Shock and non-shock stratification groups
- Shockable and non-shockable initial rhythms
- Cardiac arrest location

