# **Outcomes and Definitions**

## Primary Outcome and Sample Size Estimation

The primary outcome of the study is change in serum lactate level measured between 0-hours and 24-hours after the receipt of study drug. This outcome was chosen as lactate is a continuous variable which is highly correlated with hospital survival in cardiac arrest patients. The 24-hour time point was selected as it was drawn after completion of the rocuronium infusion but not so late that a significant proportion of patients may have already died. Based on conservative estimates drawn from observational data, a sample size of 80 patients was specified to detect a predicted mean difference in 24-hour lactate of 2.0mmol/L (±3.2mmol/L) with 80% power assuming a two-sided test and an alpha of 0.05.

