## Outcomes and Definitions

### *Primary Outcome and Sample Size Estimation*

The primary outcome of the study is change in serum lactate level measured between 0-hours and 24-hours after the receipt of study drug. This outcome was chosen as lactate is a continuous variable which is highly correlated with hospital survival in cardiac arrest patients. The 24-hour time point was selected as it was drawn after completion of the rocuronium infusion but not so late that a significant proportion of patients may have already died. Based on conservative estimates drawn from observational data, a sample size of 80 patients was specified to detect a predicted mean difference in 24-hour lactate of 2.0mmol/L ( $\pm 3.2$ mmol/L) with 80% power assuming a two-sided test and an alpha of 0.05.

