### *Analysis of Primary Outcome*

The primary outcome is lactate change between 0-hours and 24-hours after enrollment. The group difference in change from the time of study drug administration (0-hours) to 24-hours will be assessed using a linear mixed effects model. Lactate values will be log-transformed for this analysis if they are not approximately normally distributed. Fixed effects will include the allocated treatment, shock stratification, time point (0-hour, 12-hour, and 24-hour), and the interaction between treatment and time point. Study site will be included as a random intercept. The usual care group will be the reference variable for group, and baseline (0-hour) will be the

reference variable for time. Means and 95% confidence intervals of lactate over time will be presented, by treatment, using longitudinal plots (see appendix Figure 2)

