## Appendix

### *Appendix Figure 1*

*Appendix Figure 2 - Change in Lactate over Time*

*Appendix Table 1 - Cohort Characteristics*

Variable	NMB	Usual Care
Demographics		
Age (Median, IQR)		
Sex (%Female)		
Race (%White)		

Past Medical History		
Congestive heart failure		
Atrial fibrillation		
Coronary artery disease		
Prior cardiac arrest		
Chronic pulmonary disease		
Kidney disease		
Active malignancy		
Arrest Characteristics		
Location (%OHCA)		
Initial Rhythm (% Non-shockable)		
Estimated no-flow time (median, IQR)		
Estimated low-flow time (median, IQR)		
Arrest duration (minutes, median, IQR)		
Witnessed (%yes)		
Bystander CPR provided (%yes)		
Arrest etiology (%cardiac)		
Characteristics at Enrollment		
pH (median, IQR)		
pCO2 (median, IQR)		
pO2 (median, IQR)		
Shock stratification (% shock)		
STEMI present (%yes)		
Target temperature (median, IQR)		

Received any paralytic prior to enrollment (%yes)		
---	--	--

*Appendix Table 2 - Sedatives and Off-Protocol Paralytics*

Variable	NMB				Usual Care			
	0hr	12hr	24hr	36hr	0hr	12hr	24hr	36hr
Sedation and Analgesia (% receiving)								
Propofol								
Midazolam								
Lorazepam								
Dexmedetomidine								
Fentanyl								
Paralytic (% receiving)								
Bolus Rocuronium								
Continuous Rocuronium								
Bolus Cisatracurium								
Continuous Cisatracurium								

*Appendix Table 3 – Outcomes*

Variable	NMB	Usual Care	Effect estimate (95% confidence interval)
Lactate Level (mmol/L, median, IQR)			
0-hour			
12-hour			
24-hour			
36-hour			
Clinical Outcomes			
ICU LOS (days, median, IQR)			

Hospital LOS (days, median, IQR)			
Discharge CPC $\leq 2$ (%)			
Muscle Weakness Score (median, IQR)			
Hospital Survival (% survived)			

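### The subgroup plan reruns the primary analysis within each level and specifies no estimate or interval for the difference in treatment effect between levels.

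*SAP*

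**What the plan says.** The subgroup section, identical in the Protocol and the SAP, is one sentence and a list of three factors: shock stratum, initial rhythm and arrest location. The sentence reads "The primary outcome analysis will be additionally performed in each of the below subgroups".

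The analysis being repeated is the linear mixed model in Analysis of Primary Outcome. Its fixed effects are treatment, shock stratum, time point, "and the interaction between treatment and time point". Shock enters as a main effect only, and rhythm and location do not enter at all. The same section allows a change of scale: "Lactate values will be log-transformed for this analysis if they are not approximately normally distributed".

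Neither document plans a treatment-by-subgroup term, a contrast between levels or a heterogeneity test. Neither says whether the subgroup analyses are exploratory or how they are to be read. Appendix Table 3 has a column headed "Effect estimate (95% confidence interval" but no subgroup rows. The levels of arrest location are not listed; the only hint is the row "Location (%OHCA" in Appendix Table 1.

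**The concern.** The usual question for a subgroup analysis is whether the effect differs between levels. Separate fits describe the effect in each level and leave that question to the reader. Each level holds only part of an 80-patient trial, so a uniform true effect can easily give one interval that excludes zero and one that does not. That pattern is readily misread as an effect in one kind of patient and none in the other.

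What is at stake is the reading of three supporting analyses. The randomized comparison of lactate change in the whole trial is not touched.

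There is also a practical gap. The primary model cannot be rerun exactly as written inside a shock stratum, because its shock term is constant there. The sentence needs clarifying in any case.

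**Working it through.** **Inputs from the documents** (Primary Outcome and Sample Size Estimation; Randomization and Intervention): 80 patients, 1:1 allocation, difference 2.0 mmol/L, SD 3.2 mmol/L (reading the ± figure as an SD), 80% power, two-sided 0.05. The Protocol states "a sample size of 80 patients was specified to detect a predicted mean difference in 24-hour lactate of 2.0mmol/L".

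**Assumptions, because the documents are silent:** two levels per factor, 1:1 within each level, splits of 50/50, one-third/two-thirds and 20/80, the same SD in every level, no missing 24-hour values, raw scale, normal approximation. The sample-size figure concerns 24-hour lactate, whereas the analysis concerns change from 0 to 24 hours. I therefore take SD 3.2 at each time point and a 0-to-24-hour correlation ρ from 0 to 0.75. Randomization makes the expected difference in change equal to that at 24 hours.

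**Step 1. The plan's own figure.** n per arm = 2 × (1.96 + 0.8416)² × 3.2² / 2.0² = 40.2, so 41 per arm or 82 in total. With 40 per arm the power is 79.8%. The stated 80 patients reproduce.

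**Step 2. Formulas.**
- SD of change = 3.2 × √(2(1 − ρ)). At ρ = 0.5 this is 3.2, which also covers reading 3.2 as the SD of change itself.
- SE in a level with m patients per arm = SD × √(2/m).
- Power in a level: p = Φ(2.0/SE − 1.96) + Φ(−2.0/SE − 1.96).
- Exactly one level significant = p₁(1 − p₂) + p₂(1 − p₁).
- SE of the between-level difference = √(SE₁² + SE₂²); 95% half-width = 1.96 × that SE.

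Example, 50/50 and ρ = 0.5: SE = 3.2 × √(2/20) = 1.012 and p = 0.507 in each level. Exactly one significant = 2 × 0.507 × 0.493 = 0.50. SE of the difference = 1.431, half-width 2.8, power for a 2.0 mmol/L difference between levels 29%.

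**Step 3. Results at a uniform true effect of 2.0 mmol/L.**

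| Split (per-arm sizes) | ρ | SD of change | Power by level | Exactly one significant | Half-width of difference | Power for a 2.0 difference |
|---|---|---|---|---|---|---|
| 50/50 (20, 20) | 0 | 4.53 | 29%, 29% | 41% | 4.0 | 17% |
| | 0.5 | 3.20 | 51%, 51% | 50% | 2.8 | 29% |
| | 0.75 | 2.26 | 80%, 80% | 32% | 2.0 | 51% |
| 1/3, 2/3 (13.3, 26.7) | 0 | 4.53 | 21%, 36% | 42% | 4.2 | 15% |
| | 0.5 | 3.20 | 36%, 63% | 53% | 3.0 | 26% |
| | 0.75 | 2.26 | 63%, 90% | 40% | 2.1 | 46% |
| 20/80 (8, 32) | 0 | 4.53 | 14%, 42% | 45% | 5.0 | 12% |
| | 0.5 | 3.20 | 24%, 71% | 61% | 3.5 | 20% |
| | 0.75 | 2.26 | 42%, 94% | 57% | 2.5 | 35% |

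The peak can lie between the tabulated correlations. For 20/80 at ρ = 0.6 the level powers are 0.287 and 0.798, giving 0.287 × 0.202 + 0.798 × 0.713 = 0.63. For one-third/two-thirds the peak is 0.54, near ρ = 0.53 (powers 0.384 and 0.653). Over the whole range of ρ the chances are therefore about 32–50%, 40–54% and 45–63%.

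**Step 4. Dependence on the true effect.** With no effect, the chance is 2 × 0.05 × 0.95 = 0.095 for every split and correlation. At ρ = 0.5 it is 28–29% for a true effect of 1.0 mmol/L, and 27%, 35% and 53% for 3.0 mmol/L, in the same order of splits.

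**Step 5. Multiplicity of the remedy.** Three independent interaction tests at 0.05 carry 1 − 0.95³ = 14% chance of at least one false signal.

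**The case against.** The best reply is that this is one sentence about supporting analyses in a phase II trial. No decision in the documents depends on a subgroup result. The levels of a factor are separate patients, so a reader given two estimates with intervals can subtract them, and a joint model yields nearly the same contrast. The joint contrast is weak too: its half-width is as large as the planned effect or larger. All of this stands, and it keeps the point small. It does not remove it: the plan does not commit to reporting level intervals and gives no rule for reading them, and an explicit wide interval shows how little the subgroups can distinguish.

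Stronger readings are tempting, and the documents do not support them:

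- *The plan intends to claim differential effects from separate p-values.* It announces no such claim and mentions no subgroup p-values.
- *A split verdict is the most likely result.* That depends on unknown inputs. In the 50/50 case at 2.0 mmol/L, neither level is significant in 51% of trials at ρ = 0 (0.713²), against 41% for exactly one. At ρ = 0.75 both are significant in 64% (0.798²), against 32%.
- *The absence of subgroup rows in Appendix Table 3 shows they will go unreported or lack intervals.* The shell also omits listed secondary outcomes such as shock-free days and biomarkers, so it is not exhaustive.

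**Conclusion.** The point holds as a modest improvement to supporting analyses. The plan specifies no between-level estimate, interval or reading rule. That rests on the text alone and needs no calculation. The sample size reproduces, and the primary comparison is unaffected.

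The size of the risk of misreading is uncertain and should be quoted only as the ranges above. It is substantial if the true effect is uniform and near the planned 2.0 mmol/L, and about 10% if there is no effect. The ranges rest on assumed splits, an assumed correlation and equal SDs. They simplify the mixed model, whose variance components the documents do not give, and they do not apply if lactate is log-transformed.

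**What to change.** Replace the sentence in both documents with wording such as:

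> For each factor (shock vs no shock; shockable vs non-shockable rhythm; out-of-hospital vs in-hospital arrest), the primary model will be fitted to all patients with a treatment × time × subgroup term and all lower-order terms, on the same scale as the primary analysis. The 0-to-24-hour treatment effect in each level and the between-level difference will be reported with 95% CIs. These analyses are exploratory, and no differential effect will be claimed from comparing separate within-level results.

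The sponsor should confirm the two location levels, which are inferred from the baseline table shell.

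The cost is wording only; all three factors are already in Appendix Table 1. The downsides should be acknowledged:

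- The between-level difference is imprecise (half-width about 2.0–5.0 mmol/L; power about 12–51% for a 2.0 mmol/L difference), so a non-significant interaction does not show a uniform effect.
- Three tests carry about a 14% chance of at least one false signal.
- On the log scale the interaction becomes a ratio of ratios.
- Its standard error inherits the primary model's covariance structure, for which the plan names only a site random intercept.

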### *Additional Planned Analyses*

[figure not shown]
Additional planned analyses of total body oxygen consumption and cellular oxygen consumption for those patients in whom these variables are available will be performed.

### *Statistical Software*

[figure not shown]
Stata (version 14, StataCorp, College Station, Tx) will be used for all analyses.

## Appendix

### *Appendix Figure 1*

*Appendix Figure 2 - Change in Lactate over Time*

*Appendix Table 1 - Cohort Characteristics*

Variable	NMB	Usual Care
Demographics		
Age (Median, IQR)		
Sex (%Female)		
Race (%White)		

Past Medical History		
Congestive heart failure		
Atrial fibrillation		
Coronary artery disease		
Prior cardiac arrest		
Chronic pulmonary disease		
Kidney disease		
Active malignancy		
Arrest Characteristics		
Location (%OHCA)		
Initial Rhythm (% Non-shockable)		
Estimated no-flow time (median, IQR)		
Estimated low-flow time (median, IQR)		
Arrest duration (minutes, median, IQR)		
Witnessed (%yes)		
Bystander CPR provided (%yes)		
Arrest etiology (%cardiac)		
Characteristics at Enrollment		
pH (median, IQR)		
pCO2 (median, IQR)		
pO2 (median, IQR)		
Shock stratification (% shock)		
STEMI present (%yes)		
Target temperature (median, IQR)		

Received any paralytic prior to enrollment (%yes)		
---	--	--

*Appendix Table 2 - Sedatives and Off-Protocol Paralytics*

Variable	NMB				Usual Care			
	0hr	12hr	24hr	36hr	0hr	12hr	24hr	36hr
Sedation and Analgesia (% receiving)								
Propofol								
Midazolam								
Lorazepam								
Dexmedetomidine								
Fentanyl								
Paralytic (% receiving)								
Bolus Rocuronium								
Continuous Rocuronium								
Bolus Cisatracurium								
Continuous Cisatracurium								

*Appendix Table 3 – Outcomes*

Variable	NMB	Usual Care	Effect estimate (95% confidence interval)
Lactate Level (mmol/L, median, IQR)			
0-hour			
12-hour			
24-hour			
36-hour			
Clinical Outcomes			
ICU LOS (days, median, IQR)			

Hospital LOS (days, median, IQR)			
Discharge CPC $\leq 2$ (%)			
Muscle Weakness Score (median, IQR)			
Hospital Survival (% survived)			

